### 5.5.1 Handling of platelet count data

Any platelet count data obtained within 4 weeks (28 days) after the use of a rescue medication will be handled as missing in the efficacy evaluation.

In the analysis of the primary endpoint, missing data will be imputed except for data from subjects who discontinued due to an AE or lack of efficacy or those who used a rescue medication between Week 10 and Week 24. For details, see “[11.1.1 Analysis methods for the primary endpoint](#).”

## 5.6 Handling of Quality of Life Assessment (SF-36) Data

The following scores calculated based on the Japanese Version of MOS 36-Item Short-Form

Health Survey Version 2 (SF-36v2) Scoring Program will be included in the evaluation.

- Norm-based scoring (NBS)
  - Bodily pain
  - General health
  - Mental health
  - Physical functioning
  - Role emotional
  - Role physical
  - Social functioning
  - Vitality
- Three component summary scores
  - Mental component summary
  - Physical component summary
  - Role/social component summary

## 5.7 Handling of ITP Bleeding Score

The following variables calculated from 9 anatomical sites (Skin [PE], Oral [PE], Epistasis, Gastrointestinal, Urinary, Gynecological, Pulmonary, Intracranial haemorrhage, and Subconjunctival haemorrhage) will be included in the evaluation:

- Average score  
Defined as the mean of 9 sites at each time point. Handled as missing if there is a missing score for any of the sites.
- Total score  
Defined as the sum of 9 sites at each time point. Handled as missing if there is a missing score for any of the sites.
- Maximum score  
Defined as the maximum of 9 sites at each time point. Handled as missing if there is a missing score for any of the sites.
- Post-dose mean of average scores  
Defined as the mean of average scores after study drug administration in each period.

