10.5.3 Urinalysis

The following laboratory test parameters will be measured in the designated central laboratory. The presence or absence of sample collection will be recorded on the CRF.

Glucose, ketone bodies, occult blood, proteins, nitrites, bilirubin, specific gravity, pH, urobilinogen, and white blood cells

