11.3.2 Visit 4 (Week 2)

In principle, subjects should visit the study institution in the morning without taking the morning dose of the study drug.

- Study drug compliance
- ITP Bleeding Score
- Adverse events/concomitant medications
- Vital signs
- Laboratory tests (hematology and serum chemistry)
- Pharmacokinetics (before study drug administration)
- Study drug dispensed (Period I)^{a)}
- Administration of study drug
- Pharmacokinetics (1 to 4 hours after study drug administration)
- a) The need of dispensing the study drug is decided, considering the number of tablets to be taken before the next visit.

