14.6.2 ITP Bleeding Score

1) Summary statistics will be presented for the mean and total scores of the anatomical sites (9 sites except Skin [Hx] and Oral [Hx]) and distribution of the maximum score will be presented.

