Appendix 2 Immune Thrombocytopenic Purpura Bleeding Scale

	Bleeding score					
Site	0	1	2			
Skin (Physical Examination	None	1–5 bruises and/or	> 5 bruises with size			
[PE])		scattered petechiae	> 2 cm and/or diffuse			
			petechiae			
Oral (PE)	None	1 blood blister or	Multiple blood blisters			
		> 5 petechiae or gum	and/or gum bleeding			
		bleeding that clears				
		easily with rinsing				
Skin (Hx)	None	1–5 bruises and/or	> 5 bruises with size			
		scattered petechiae	> 2 cm and/or diffuse			
			petechiae			
Oral (Hx)	None	1 blood blister or	Multiple blood blisters			
		> 5 petechiae and/or	and/or gum bleeding			
		gum bleeding < 5 min	> 5 min			
Epistasis None		Blood when blowing nose and/or epistaxis	Bleeding > 5 min (per			
			episode)			
G 1 (GD)		< 5 min (per episode)	G 11 1			
Gastrointestinal (GI)	None	Occult blood	Gross blood			
Urinary (U)	None	Microscopic	Macroscopic			
G 1 1 (GVD)	NT (1 ' 1)	(+ve dipstick)	D1 1' ' ''			
Gynecological (GYN)	None (normal period)	Spotting not at time of	Bleeding > spotting			
		normal period	not at time of period			
D. I	NT.	37/4	or very heavy period			
Pulmonary	None	N/A	Yes			
Intracranial haemorrhage	None	N/A	Yes			
Subconjunctival haemorrhage	None	Yes	N/A			

Source:

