## 1) Evaluation in Period I

**Table 5.9-1 Analysis Visits in Period I**

Variables evaluated	Analysis visit
Platelets	Screening A, B, Day 1, Week 2 to 24 (every 2 weeks)
Treatment dose	Day 1, Week 2 to 24 (every 2 weeks)
QOL assessment (SF-36)	Day 1, Week 4, 12, 24
ITP Bleeding Score	Screening A, Day 1, Week 2 to 24 (every 2 weeks), LOV
ECOG Performance Status	Screening A, Day 1, Week 4 to 24 (every 4 weeks), LOV
Hematology (excluding platelets)	Screening A, B, Day 1, Week 2 to 24 (every 2 weeks), LOV
Serum chemistry	Screening A, Day 1, Week 2 to 24 (every 2 weeks), LOV
Urinalysis	Screening A, Day 1, Week 4 to 24 (every 4 weeks), LOV
Immunoglobulin test	Screening A, Day 1, Week 24, LOV
Vital signs	Screening A, B, Day 1, Week 2 to 24 (every 2 weeks), LOV
Plasma drug concentration	Pre-study drug administration: Week 2, 6; Post-study drug administration: Week 2 to 24 (every 2 weeks)

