### 3) Evaluation in Period II

The following data will be used as Week 24 to 52 data:

- Data from Week 24 to 52 of subjects who received placebo in Period I, completed Period I, and transitioned to Period II.
- Data from early transition Day 1 to early transition Week 28 of subjects who discontinued Period I and early transitioned to Period II.

**Table 5.9-5** Analysis Visits in Period II

Variables evaluated	Analysis visit
Platelets	Week 24 to 52 (every 4 weeks)
Treatment dose	Week 24 to 52 (every 4 weeks)
QOL assessment (SF-36)	Week 24, Week 52
ITP Bleeding Score	Week 24 to 52 (every 4 weeks), LOV
ECOG Performance Status	Week 24 to 52 (every 4 weeks), LOV
Hematology (excluding platelets)	Week 24 to 52 (every 4 weeks), LOV
Serum chemistry	Week 24 to 52 (every 4 weeks), LOV
Urinalysis	Week 24, Week 28 to 52 (every 12 weeks), LOV
Immunoglobulin test	Week 24, Week 52, LOV
Vital signs	Week 24 to 52 (every 4 weeks), LOV

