## 6.2 Handling of Dropouts and Missing Data

When data to be used for analysis are missing, they will be handled as missing, and no statistical imputation will be performed, excluding the variables listed in “[5 Data Handling](#)” and below. Last observation carried forward (LOCF) imputation will be applied to the primary endpoint. For details, see “[11.1 Primary Endpoint](#).”

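### The SAP sets the maximum ITP Bleeding Score to missing when any of 9 sites is unscored, even when a recorded grade 2 already fixes it

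*SAP*

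**What the plan says.** Protocol 14.6.2 bases the score on "9 sites except Skin [Hx] and Oral [Hx"], and SAP 5.7 lists the same nine. The protocol has no rule for an unscored site. The SAP adds one. For the maximum it reads "Defined as the maximum of 9 sites at each time point. Handled as missing if there is a missing score for any of the sites", and the average and total are treated the same way. SAP 6.2 does not rescue a partly scored visit: outside the exceptions it names, when data are missing "they will be handled as missing, and no statistical imputation will be performed".

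SAP 12.2 reports the maximum as numbers and percentages of subjects, and the average, total and post-dose mean of averages as summary statistics.

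On the scale (Protocol Appendix 2), every site runs from 0 to at most 2. Pulmonary and intracranial bleeding have no grade 1. Urinary grade 1 requires a positive dipstick. Gynecological grade 0 is worded "None (normal period"), with no instruction for men.

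On the schedule, the score is taken every 2 weeks in Period I and every 4 weeks in Period II. The urinalysis row reads "Screening A, Day 1, Week 4 to 24 (every 4 weeks), LOV" in SAP Table 5.9-1 and "Week 24, Week 28 to 52 (every 12 weeks), LOV" in Table 5.9-5. The Week 2 visit in Protocol 11.3.2 lists only "Laboratory tests (hematology and serum chemistry"). Protocol 10.5.3 says of urinalysis: "The following laboratory test parameters will be measured in the designated central laboratory".

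**The concern.** An all-or-nothing rule can be defended for a sum or a mean, where a blank site leaves the value unknown. It is harder to defend for a maximum on a scale capped at 2. Once a 2 is recorded the answer is known, and discarding it removes information that the investigator has already supplied. The bleeds concerned are the most serious on the scale. Protocol 5.2.1, criterion 9, excludes anyone with a grade 2 at any site at Screening A or Day 1, so in an eligible subject a later grade 2 is new since Day 1.

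The score is a named safety endpoint, chosen because of the disease (Protocol 4.2.2). With 24 planned subjects, one subject moves a percentage visibly.

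A second question follows from the same rule. One site does not apply to men, and grade 1 at another needs a test that is not scheduled at every scoring visit. Neither document says how these sites are entered, so the reach of the rule cannot be read from the plan.

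**Working it through.** The documents give no figure to reproduce. The check is logic plus visit counts.

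**1. The maximum.** Let M be the highest observed site score and x the score at the unscored site, with x at most 2. The true maximum is max(M, x).

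- If M = 2, then max(2, x) = 2 for x = 0, 1 or 2. The value is known, yet SAP 5.7 returns missing.
- If M is 0 or 1, the true maximum is at least M. The observed maximum is then a lower bound.

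Example: intracranial = 2, seven sites = 0, one site blank. The maximum is 2; the SAP value is missing.

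**2. Effect on one cell of the SAP 12.2 table.** Inputs are the planned 16 and 8 subjects (Protocol 8.9.1). Assume that all attend, that all other scores are complete, and that one subject has a grade 2 with one blank site.

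- R788: 1/16 = 6.3% is reported as 0/15 = 0%.
- Placebo: 1/8 = 12.5% is reported as 0/7 = 0%.

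**3. Scoring visits without a scheduled urinalysis.** Inputs are SAP Tables 5.9-1 and 5.9-5, checked against the visit lists in Protocol 11.3 to 11.7.

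| Period (post-dose) | Scoring visits | With urinalysis | Without |
|---|---|---|---|
| I | 12 (Weeks 2 to 24) | 6 (Weeks 4, 8, 12, 16, 20, 24) | 6/12 = 50% |
| II | 7 (Weeks 28 to 52) | 3 (Weeks 28, 40, 52) | 4/7 = 57% |
| I and II | 19 | 9 | 10/19 = 53% |

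In the non-dosing period and Period III, urinalysis is listed at every scoring visit, so the mismatch does not arise there.

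**4. What the rule does under each coding (Period I).** Planned post-dose scores: 24 × 12 = 288.

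- *Untested Urinary site left blank:* 288 × 0.5 = 144 lost.
- *Gynecological site left blank in men:* 288 × m lost, where m is the share of men. The documents do not give m. For an assumed m = 0.25 this is 72, and for m = 0.5 it is 144.
- *Both left blank:* 288 × [m + (1 − m) × 0.5]. This gives 144 (m = 0), 180 (m = 0.25), 216 (m = 0.5) and 288 (m = 1).
- *Both coded 0:* none lost. A microscopic haematuria that is not tested for lowers the total by 1 and the average by 1/9 = 0.11. In men the total and maximum are unaffected by the Gynecological 0; the average is 8/9 of what it would be over eight sites (11% lower).

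**5. Why keeping only the known 2s is not enough.** At one time point, let n subjects be fully scored, a of them with a 2, and let k be partly scored, b of them with a 2. Keeping a partly scored subject only when a 2 is seen gives (a + b)/(n + b). Keeping all of them gives (a + b)/(n + k). Since b cannot exceed k, the former is never smaller, and it is larger whenever some partly scored subject has no 2. Missingness would depend on the outcome.

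**The case against.** The strongest reply is that nothing in the documents shows any site being left blank. The investigator scores the scale (Protocol 10.13), and None is an available answer at both the Gynecological and the Urinary site. A man without gynecological bleeding fits it naturally; the bracketed words can be read as saying that normal menses also count as 0. SAP version 3.0 lists 14 changes, none to section 5.7, and one might expect a correction had all men's scores come out missing. That is weak evidence, but it points away from widespread blanks. This part of the reply stands.

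A reader might therefore infer too much in four ways:

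- **That half of the visits, or all men, are lost.** The counts in the working are worst cases that depend on case report form coding the documents do not show.
- **That the urinalysis result is not available when the site is scored.** Protocol 10.5.3 says only that a central laboratory measures it. Protocol 10.13 does not say when the score is finalised, and a local dipstick is not forbidden.
- **That this is the only systematic bleeding measure.** Bleeding adverse events are of special interest (Protocol 10.15.5, SAP 5.3), and urine occult blood is summarised separately (SAP 12.4). Adverse events are not a full substitute, because Protocol 10.15.1.3, item 10, leaves out worsening within the range expected for the disease.
- **That the arms are biased against each other.** Both Period I arms share one schedule, and SAP 12.2 plans no test.

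None of this answers the point about the maximum. That rule is explicit and discards a known value whatever the reason for the blank.

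**Conclusion.** The point holds for the maximum score without any assumption about coding: SAP 5.7 sets to missing a value that an observed grade 2 already determines. It has an effect only if a visit has both a recorded 2 and a blank site, and the documents give no frequency for that. When it occurs, one subject is worth about 6 percentage points in the R788 arm or 12.5 in the placebo arm at that time point, under the planned numbers and otherwise complete scores.

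For the Gynecological and Urinary sites the conclusion is conditional. If they are left blank, the rule removes the average, total and maximum for men and at the 6 of 12 and 4 of 7 post-dose visits without scheduled urinalysis. If they are coded 0, no visit is lost, but microscopic haematuria cannot be scored at those visits without an unscheduled test. The plan should say how the rule applies rather than leave this open.

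The endpoint is a descriptive safety endpoint. The primary analysis is unaffected.

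**What to change.** Amend SAP 5.7, with matching output under 12.2:

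1. Define the maximum as the highest score among the observed sites at every visit with at least one site scored. Report the number of partly scored visits beside it. Applying this to all partly scored visits, not just those with a 2, keeps the grade 2 percentage from being inflated.
2. State that the Gynecological site in men does not trigger the missing rule and counts as 0. This keeps the protocol's nine sites and one divisor for both sexes.
3. As a descriptive supplement, show average and total scores separately for visits with and without a scheduled urinalysis.

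The cost is SAP wording and some programming, with no new data or visits. The downside is that the maximum at a partly scored visit with no 2 is a lower bound, which is why the count of such visits should be shown. Counting 0 in men leaves their average over nine sites rather than eight, as in the working.

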## 5.8 Handling of Blood Pressure Data

At analysis visits where blood pressure is measured multiple times, the mean blood pressure value will be used for evaluation.

## 5.9 Analysis Visits

Unless otherwise specified, each analysis variable will be evaluated at the following time points.

- Data obtained outside the time window of analysis visits and data from unscheduled visits

will be excluded from summarization at each time point.

- For analyses of each treatment period, test data obtained outside the range of “the day of the last dose plus the specified number of days” will be excluded from the analysis. The specified number of days is 3 days for Period I and 7 days for Periods II and III.
- The last observed visit (LOV) other than the non-dosing period is defined as the last scheduled visit or the discontinuation visit, whichever is later, performed within the range of “the day of the last dose plus the specified number of days” for each period. The specified number of days is 3 days for Period I and 7 days for Periods II and III.
- The LOV in the non-dosing period is defined as the data for the latest test among all tests performed up to the last day of the non-dosing period.
- For all variables, Day 1 of Period I will be used as a baseline and only changes at time points after Day 1 of each period will be evaluated.
- In the non-dosing period, change from the start of the non-dosing period will be evaluated in addition to the change from Period I Day 1. Time points after Day 1 of the non-dosing period will be evaluated.

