3.2 Secondary Objectives

- 1) To evaluate the efficacy of R788 in patients with chronic ITP for the following points:
 - Maintenance of platelet count during long-term treatment with R788
 - Increase in platelet count during Period II for patients who received placebo in Period I
 - Improving of QOL
- 2) To investigate the safety of R788 in patients with chronic ITP
- 3) To investigate the pharmacokinetics of R788 in patients with chronic ITP (Period I).

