5.1 Inclusion Criteria

5.1.1 Inclusion criteria

- 1) Japanese patients (defined as Japanese whose all relatives within the second degree are Japanese) who give written informed consent to participate in the study
- 2) Patients at least 20 years of age (at the time of informed consent)
- 3) Patients diagnosed with ITP according to the ITP diagnostic criteria (revised in 1990)¹⁾ by the Study Group on Idiopathic Hematopoietic Disorders of the Ministry of Health, Labour and Welfare at least 6 months before acquisition of consent
- 4) Patients with a platelet count average of < 30000/μL at Screen A, Screen B, and Day 1. Each platelet count should not exceed 35000/μL.
- 5) Patients who have used and failed or who were intolerant at least 1 of the following typical regimen for the treatment of ITP before informed consent
 - Corticosteroids
 - TPO receptor agonists (eltrombopag olamine or romiplostim)
 - Rituximab
 - Intravenous immunoglobulin
- 6) Patients with ECOG performance status of 0 or 1 at Screening A and Day 1

7) Patients who do not use treatment for ITP or patients whose concurrent treatment may consist of either corticosteroids (equivalent to 10 mg/day prednisolone or less), azathioprine, or danazol. The dose of the concurrent medication must have been stable for at least 2 weeks prior to Day 1 and must be expected to remain stable throughout Period I.

- 8) Patients who can discontinue or have already discontinued the following ITP drugs for at least the following periods prior to Day 1, if applicable
 - Cyclosporine or mycophenolate mofetil: 2 weeks

• Eltrombopag olamine: 2 weeks

• Romiplostim: 3 weeks

• Alkylating agent: 8 weeks

- Rituximab or other anti-CD20 monoclonal antibodies: 24 weeks
- 9) Patients who are negative for *H. pylori* or who have completed *H. pylori* eradication therapy

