14.5.2.3 Evaluation in Period II

The data in Periods I and II from subjects who receive placebo in Period I and transition to Period II will be analyzed as described in 1). The data in Period II from early transition subjects after completing the treatment with R788 in Period I and those who receive placebo in Period I

and transition to Period II will be analyzed by groups, as specified in 2) to 7). The periods from Weeks 24 to 52 and from ET Day 1 to ET Week 28 will be hereinafter expressed as Day 1 to Week 28 of Period II and Day 1 of Period II will be considered as the baseline of Period II.

1) Achievement rate of maintenance of platelet count in Periods I and II

Considering the subjects who achieve a platelet count of $\geq 50000/\mu L$ within 12 weeks after the start of study treatment in Periods I and II and maintain it for 12 weeks as a responder, the achievement rate with two-sided 95% exact confidence interval (Clopper-Pearson) will be presented. The difference in the achievement rate between Periods I and II and its two-sided 95% exact confidence interval will be presented. McNemar test will be used to evaluate the difference in the achievement rate between Periods I and II.

2) Achievement rate of platelet count

The achievement rate with two-sided 95% exact confidence interval (Clopper-Pearson) will be presented for the following endpoints. Any subject not evaluated as a responder will be regarded as a non-responder.

- Achievement rate of platelet count of $\geq 50000/\mu L$ at Weeks 12, 24, and 28 in Period II
- Achievement rate of a platelet count increase at least 20000/μL above baseline and ≥ 30000/μL at Weeks 12, 24, and 28 in Period II (for subjects with a baseline platelet count of < 15000/μL)
- 3) Duration of stable platelet response

Summary statistics will be presented for the duration of stable platelet response from the first achievement of a platelet count of $\geq 50000/\mu L$ after administration of the study drug in Period II.

- 4) Summary statistics will be presented for the measured value of platelet count and change from the baseline.
- 5) Frequency distributions of platelet count will be presented.
- 6) The time course of platelet count in individual subjects will be presented.
- 7) The summary statistics of the QOL evaluation (SF-36) will be presented.

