14.6 Safety

SS will be used as the safety analysis set. Safety will be analyzed by the analysis groups and Day 1 of each period will be considered as the baseline. Day 1 of Period I will be considered as the baseline for the evaluation of the long-term administration of R788. In addition, the analysis for the Non-dosing period and Period III will be performed only for "14.6.1 Adverse events and adverse drug reactions" and "14.6.2 ITP Bleeding Score", and the analysis for R788 treatment period will be performed only for "14.6.1 Adverse events and adverse drug reactions."

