## 3. Analysis Group

Unless otherwise specified, the analysis will be performed on the following subjects and data. For FAS analysis, “treated subjects” will be handled as “randomized subjects.”

- 1) Evaluation in Period I
  - R788 group: Period I data of subjects who received R788 in Period I
  - Placebo group: Period I data of subjects who received placebo in Period I
- 2) Evaluation during long-term treatment of R788
  - R788 group: The analysis will be performed on the following subjects and data:
    - Period I data of subjects who received R788 in Period I
    - Period II data of subjects who received R788 in Period I, completed treatment with R788 in Period I and transitioned to Period II (subjects on long-term treatment of R788)

3) Evaluation in Period II

- R788-R788 group: Period II data of subjects who received R788 in Period I and early transitioned to Period II after discontinuing Period I
- P-R788 group: Period II data of subjects who received placebo in Period I and transitioned to Period II

4) Evaluation in non-dosing period

- R788 group: Non-dosing period data of subjects who transitioned to the non-dosing period (subjects who transitioned from Period II to Period III without non-dosing period are excluded).

5) Evaluation in Period III

- R788 group: Period III data of subjects who transitioned to Period III

6) Evaluation in R788 treatment period

- R788 group: The analysis will be performed on the following subjects and data:
  - Data from Period I, Period II, and Period III of subjects who received R788 in Period I
  - Data from Period II and Period III of subjects who received placebo in Period I and transitioned to Period II

7) Evaluation in the entire study period

- R788-R788 group: Data from Period I, Period II, non-dosing period, and Period III of subjects who received R788 in Period I
- P-R788 group: Data from Period I, Period II, non-dosing period, and Period III of subjects who received placebo in Period I

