## 16. Changes from the Protocol

### 16.1 Changes in Statistical Analysis Plan Version 1.0

- 1) In “[3 Analysis Group](#),” the “period I data of subjects who discontinued R788 treatment in Period I” were added to the evaluation during long-term treatment of R788.

Reason: The purpose of this analysis was to evaluate the efficacy and safety of R788 from the start to the end of treatment with the product. Therefore, it was considered appropriate to include subjects who discontinued Period I in the analysis.

- 2) In “[3 Analysis Group](#),” evaluation in the entire study period was added.

Reason: To evaluate platelet response throughout the entire period after study entry.

- 3) In “[5.9 Analysis Visits](#),” the baseline for change calculation was defined as Day 1 of Period I for all periods.

Reason: In the protocol, the baseline was defined as Day 1 of each period. However, it was considered appropriate to use the value not affected by study drug administration as the baseline value.

- 4) In “[6.3.1 Timing of analysis](#),” the scope of data to be cutoff was changed, and variables to be analyzed were clarified.

Reason: To include Period II data in the first data cutoff and the non-dosing period data in the second data cutoff. In addition, variables to be analyzed at the time of cutoff were clarified.

- 5) Evaluation of line of therapy-related variables was added to “[9.1 Subject Demographics](#),” and evaluation of achievement rate of platelet-related endpoints was added to “[11.2.6.1 Platelet response rate](#)” and “[11.3 Subgroup Analysis of Efficacy](#).”

Reason: To evaluate the effect of line of therapy on efficacy, as evaluated in the paper of foreign studies.

- 6) In “[7 Definition of Derived Data](#),” the definition of the start day of platelet response was changed to “the first day after the start of study treatment in each period on which a platelet count of  $\geq 50000/\mu\text{L}$  for at least 28 consecutive days without the use of rescue medications was achieved.”

Reason: To evaluate stable maintenance of platelet count.

- 7) In “[11.1 Primary Endpoint](#),” sensitivity analysis of the primary endpoint planned in the protocol was deleted.

Reason: A blind review confirmed that no subject would need imputation of missing

platelet count data for the evaluation of stable platelet response. It was thus decided not to perform sensitivity analysis because no imputation would be performed.

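### Period II platelet change in placebo switchers is measured only from Period I Day 1, so it does not isolate the increase during Period II

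*SAP*

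**What the plan says.** Protocol 3.2 lists as a secondary objective: "Increase in platelet count during Period II for patients who received placebo in Period I". For the Period II efficacy analyses, Protocol 14.5.2.3 says "Day 1 of Period II will be considered as the baseline of Period II". Protocol 14.6 follows the same principle for safety, apart from the long-term evaluation: "Safety will be analyzed by the analysis groups and Day 1 of each period will be considered as the baseline".

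SAP 5.9 replaces this with "For all variables, Day 1 of Period I will be used as a baseline" and adds that "only changes at time points after Day 1 of each period will be evaluated". SAP 16.1 item 3 declares the change and gives one reason: "it was considered appropriate to use the value not affected by study drug administration as the baseline value".

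SAP 3 defines the switchers as "P-R788 group: Period II data of subjects who received placebo in Period I and transitioned to Period II". Three of their Period II efficacy outputs use the baseline:
- 11.2.3.4, summary statistics of platelet change;
- 11.2.3.5, change below 20,000/µL or at least 20,000/µL;
- 11.2.3.2, second item: at least 30,000/µL with a rise of at least 20,000/µL, in subjects with a baseline below 15,000/µL.

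For the non-dosing period only, SAP 5.9 and 11.2.4.1 show change from the start of that period as well as from Period I Day 1.

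**The concern.** The reason in SAP 16.1 fits subjects who took R788 in Period I, whose later counts may reflect the drug. It does not fit P-R788. Their Week 24 or ET Day 1 count follows placebo only and is the last count before R788 starts. Their Period I Day 1 count is about 12 to 24 weeks older.

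That older count was also chosen to be low. Inclusion criterion 4 requires a mean below 30,000/µL "at Screen A, Screen B, and Day 1. Each platelet count should not exceed" 35,000/µL, so Day 1 is itself one of the selecting measurements and some later rise is expected without treatment. Protocol 1.2 also reports spontaneous recovery in 5% to 10% of untreated patients.

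A change from Period I Day 1 therefore adds the placebo period to the R788 period, whereas the objective asks about Period II alone. The subset below 15,000/µL is likewise fixed on a count that may no longer describe the subject when R788 starts.

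**Working it through.** **Plan's own figure.** The documents give none on this point. Their one design figure, 89% (Protocol 8.9.2), concerns the primary endpoint and does not depend on the baseline. It reproduces: P(X₁/16 > X₂/8), with X₁ ~ Bin(16, 0.178) and X₂ ~ Bin(8, 0.02), is 0.8932.

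**Decomposition.** For a completer at Week 36:

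Week 36 − Period I Day 1 = (Week 24 − Period I Day 1) + (Week 36 − Week 24).

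The first bracket is placebo time and the second is R788 time. Any drift on placebo, up or down, enters the SAP's change one for one and does not enter the protocol's.

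**Invented example.** Counts of 12,000, 26,000 and 33,000/µL at Period I Day 1, Week 24 and Week 36.
- SAP: baseline below 15,000; 33,000 − 12,000 = +21,000; a responder.
- Rise on R788: 33,000 − 26,000 = +7,000. By the Week 24 count, the subject is outside the subset.

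**Regression to the mean alone.** The documents give no within-subject platelet SD, so all variances here are assumptions. Counts were simulated with no drug effect and no drift, and inclusion criterion 4 was applied to three screening counts. The first set of runs used log-normal counts with between-subject log-SD 0.4. The rate is the rise-based responder rate, with the subset below 15,000/µL defined on whichever baseline is used.

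| Median (/µL) | Within-subject log-SD | Mean change from Period I Day 1 (/µL) | Mean change from Week 24 | Rate, Period I Day 1 | Rate, Week 24 |
|---|---|---|---|---|---|
| 20,000 | 0.3 | +900 | about 0 | 1.4% | 1.4% |
| 20,000 | 0.5 | +3,000 | about 0 | 9.1% | 8.2% |
| 20,000 | 0.7 | +6,500 | about 0 | 17.1% | 15.9% |
| 25,000 | 0.3 | +1,500 | about 0 | 2.4% | 2.3% |
| 25,000 | 0.5 | +4,400 | about 0 | 12.9% | 11.7% |
| 25,000 | 0.7 | +9,000 | about 0 | 22.4% | 20.6% |
| 30,000 | 0.3 | +2,000 | about 0 | 3.7% | 3.3% |
| 30,000 | 0.5 | +5,800 | about 0 | 17.1% | 15.2% |
| 30,000 | 0.7 | +11,500 | about 0 | 27.4% | 25.0% |

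The second set used normal counts: mean 20,000 to 25,000, between-subject SD 8,000 to 10,000 and within-subject SD 5,000 to 8,000/µL. Change from Period I Day 1 averages about +250 to +1,400/µL overall and +2,500 to +7,600/µL in the subset. Of subjects below 15,000 at Period I Day 1, 28% to 56% are at or above it at Week 24.

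**Why the rate barely moves.** Restricting to a low count brings regression to the mean whichever count is used, so both versions of the subset carry it. The largest gap is 27.4 − 25.0 = 2.4 percentage points. Even if all 8 planned placebo subjects were in the subset, that is 0.024 × 8 ≈ 0.2 of a subject.

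**Early transition.** Protocol 8.3.1 admits early-transition subjects because their counts are low. Approximating this in the log-normal runs by a last count below 50,000/µL gives +800 to +10,600/µL from Period I Day 1 and +100 to +7,100/µL from Period II Day 1. The later baseline reduces the artefact but does not remove it.

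**The case against.** The strongest reply is that the main analysis of switchers does not use a baseline. SAP 11.2.3.1 compares sustained response at 50,000/µL between Periods I and II within subject by McNemar test. The 50,000/µL rates at Weeks 36, 48 and 52 and the duration of response also use absolute thresholds. SAP 6.5.2 treats everything except the primary endpoint as reference only. All of this stands, and no test result or error rate changes.

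The placebo part is also partly visible. Platelet counts are tabulated from Week 24, with ET Day 1 mapped to it (SAP 5.9), and individual courses are plotted. This stands for group means. It does not give the distribution of changes on R788, the change categories or the rise-based rate.

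A common pre-study baseline is declared and defensible, and Protocol 5.3.1 itself refers to a rise from Day 1 when judging benefit in Periods II and III. A Period II baseline has weaknesses too. ET Day 1 is selected to be low. It may follow rescue treatment, in which case SAP 5.5.1 sets it to missing for 28 days. It can also mislead the other way: 22,000 falling to 12,000 on placebo and then reaching 33,000/µL scores +21,000, but only +11,000 above entry. These points argue against discarding Period I Day 1. They do not argue against showing both.

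A reader might infer that the switcher results are materially inflated in favor of R788, or that many responders are false. The documents do not support that. They give no variances, the simulated mean shift runs from negligible to large, true drift could go either way, and the rise-based rate hardly moves through selection alone. A reader might also infer that the baseline should simply be replaced in P-R788. That would give the between-group difference in SAP 11.2.3.2 two baselines and two different subsets.

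**Conclusion.** The point holds as a limited one. For P-R788, the reason given in SAP 16.1 does not justify dropping the protocol's baseline. As a result, the three change-based outputs do not isolate the increase during Period II named in Protocol 3.2. The mixture of placebo and R788 time follows directly from the definitions and needs no assumption. Its size does: about +250 to +11,500/µL on the mean across the assumed variances, with no drift, and at most 2.4 percentage points on the rise-based rate in the log-normal runs. Real drift would add to or subtract from the mean shift. The consequence is for the interpretation of descriptive tables in a planned group of 8.

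**What to change.** In SAP 5.9, define a second baseline for P-R788: the last valid platelet count before the first R788 dose. This is the Week 24 or ET Day 1 count or, if that count is set to missing under the 28-day rescue rule, the last earlier valid one. In 11.2.3.4 and 11.2.3.5, show change from this count beside change from Period I Day 1. In 11.2.3.2, add the rise-based rate with the subset below 15,000/µL defined on the same count. State that the Period II objective is read from these results. Keep Period I Day 1 as the common baseline for the difference between R788-R788 and P-R788. This extends to Period II what the SAP already does for the non-dosing period.

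The cost is one derived variable, a few table columns and a sentence of SAP text. A footnote should say that early-transition subjects still carry some regression to the mean at ET Day 1, because they enter on low counts.
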